Thirty-two potential participants received a face-to-face screening assessment. A sample of 32 eligible participants were randomized into the mCIMT or control group by permuted block randomization with block length 4 (N=16 per group). The evaluations were performed on two occasions: at baseline and immediately after the intervention. Only children in the control group who participated in the accelerometer study (N=4) underwent an additional evaluation to determine whether changes in the values of accelerometers were due to mCIMT or whether they changed as they grew older. The measures were conducted by occupational and physical therapists with more than 10 years of experience who were blinded to the intervention.

Modified constraint-induced movement therapy (mCIMT)

Each child in the mCIMT group wore an individually tailored plastic forearm resting splint that is detachable on his or her non-paretic side for 3 weeks. The therapist removed the splint for 15 minutes before each mCIMT session to allow for active range of motion of the non-paretic upper limb and to assess non-paretic hand function by the grasping domains of PDMS-2. The participants could take off the splints during washes and while in sleep. In addition, parents were asked to take off the splints and report if adverse events such as increase of stress/crying, sleep disorders, or skin rashes occurred. A standardized pediatric CIMT protocol, which is a technique to shape motor behavior with repetitive and concentrated training of the paretic upper limb according to Taub's and Deluca's protocol,^{15,16} was applied by an occupational therapist. The 15 treatment sessions occurred over a 3-week

period (excluding weekends) in the mCIMT group, for 2 hours each (30-hour dosage in total). The control group received no mCIMT protocol except for children who wore accelerometers; they received mCIMT protocol post-test. All subjects who participated in this study retained the occupational or physical therapy they received.

Statistical analyses plan

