Baseline characteristics between the mCIMT and control groups will be compared using independent t-test, chi-square test, and Fisher's exact test. Differences between groups in standardized assessments at post-treatment will be compared with analysis of covariance using pre-treatment measures as covariates to determine the effect of mCIMT treatment. In addition, pre- and post-treatment outcomes of standard assessments will be compared using paired t-test in each group, and Wilcoxon signed-rank test was performed to compare pre- and post-treatment accelerometer outcomes (VMA, %MVPA, UR) of the eight children. Effect sizes will be expressed as partial eta-squared, which was calculated and reported as recommended by Cohen.¹⁷ The ranges for effect sizes are small ($.01 < \eta^2 < .06$), moderate ($.06 < \eta^2 < .14$), and large ($\eta^2 > .14$). Data analyses will be conducted using IBM SPSS Statistics for Windows, version 21.0 (IBM Corp., Armonk, NY).

References

2. Johnson A. Prevalence and characteristics of children with cerebral palsy in Europe. *Dev Med Child Neurol* 2002;44:633–640

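### The one accelerometer test stated is an uncontrolled before-after test of eight children, so it cannot separate mCIMT from growth, which is why four controls had an extra evaluation

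*Combined protocol and SAP*

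**What the plan says.** **Accelerometer test.** Statistical analyses plan: "Wilcoxon signed-rank test was performed to compare pre- and post-treatment accelerometer outcomes (VMA, %MVPA, UR) of the eight children".

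**Other tests.** The same section ties the between-group analysis to a different set of outcomes: "Differences between groups in standardized assessments at post-treatment will be compared with analysis of covariance". The within-group tests are tied likewise: "pre- and post-treatment outcomes of standard assessments will be compared using paired t-test in each group".

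**Evaluations.** Study design sets the general schedule: "The evaluations were performed on two occasions: at baseline and immediately after the intervention". It then adds an exception: "Only children in the control group who participated in the accelerometer study (N=4) underwent an additional evaluation", with the purpose "to determine whether changes in the values of accelerometers were due to mCIMT or whether they changed as they grew older".

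**Treatment of the controls.** The mCIMT section says of the control children with accelerometers that "they received mCIMT protocol post-test". Of the whole sample it says: "All subjects who participated in this study retained the occupational or physical therapy they received".

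The documents do not state who the eight are, how many mCIMT children wore accelerometers, when the extra evaluation took place, or which evaluation counts as pre-treatment for the controls.

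**The concern.** A one-sample before-after test measures total change. In children aged 7 to 36 months, that total contains growth and the effect of the therapy they kept, as well as any effect of mCIMT. The investigators foresaw this and gave four controls an extra evaluation to deal with it, but the analysis section never uses an untreated interval. Followed as written, the plan leaves its own question open.

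This bears on a main aim. Study Objective asks whether mCIMT raises real-world use of the paretic arm. Background argues that the parent-rated log may be subjective and that capacity tests do not measure real-world use. By the document's own reasoning, the accelerometer supplies the objective evidence, and its only stated test is uncontrolled.

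**Working it through.** There is no planned figure to reproduce: the documents give no alpha, SD, effect size or sample-size calculation. I assume a two-sided 0.05 level and normally distributed changes, measured in units of the SD of change.

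**1. Which stated analysis has a comparator?**

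| Analysis | Outcomes | Untreated comparator |
|---|---|---|
| ANCOVA | standardized assessments | yes (16 v 16) |
| Paired t-test per group | standard assessments | no |
| Signed-rank, n = 8 | VMA, %MVPA, UR | no |

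One sentence gives the paired t-test to the standard assessments and the signed-rank test to the accelerometer. Background also treats standardized motor tests and accelerometry as different kinds of measure. The ANCOVA therefore does not cover the accelerometer.

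**2. The stated test under drift alone.** With n = 8 there are 2^8 = 256 sign patterns. Those giving W = 0, 1, 2, 3 number 1 + 1 + 1 + 2 = 5, so rejecting at W ≤ 3 or W ≥ 33 has size 2 × 5/256 = 10/256 = 3.9%. The next level is 14/256 = 5.5%. Simulated rejection with no mCIMT effect:

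| Assumed drift (SD of change) | Rejection |
|---|---|
| 0 | 3.9% |
| 0.1 | 4.5% |
| 0.25 | 7.5% |
| 0.5 (illustration only) | 19% |
| 1.0 (illustration only) | 61% |

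Suppose four of the eight are controls and their pre-treatment value is their baseline, so that their change spans two intervals of equal length and SD. Then 4.5% becomes 5.2% at 0.1 SD per interval, and 7.5% becomes 12% at 0.25 SD.

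**3. Which intervals exist?** The controls were probably seen at baseline, at post-test and again after their later mCIMT. On that order, the two routine evaluations bound an untreated interval and the extra one closes a treated interval. If the extra evaluation instead came just before their mCIMT, one untreated and one treated interval still result. Either order is inference.

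**4. What could a treated-versus-untreated comparison deliver?** The group sizes are not stated: N = 4 is given for controls only. Two readings are four mCIMT children plus the four controls (4 v 4), or eight mCIMT children compared with four separate controls (8 v 4). For the exact rank-sum test:

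| | 4 v 4 | 8 v 4 |
|---|---|---|
| Allocations | C(8,4) = 70 | C(12,4) = 495 |
| Smallest two-sided p | 2/70 = 0.0286 | 2/495 = 0.004 |
| Bonferroni at 0.05/3 = 0.0167 | cannot reject | can reject |
| Power at 1, 2, 3 SD | 14%, 49%, 83% | 29%, 80%, 98% |

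At 4 v 4 the next attainable p is 4/70 = 0.057, so only complete separation rejects. The exact Hodges-Lehmann interval has coverage 1 − 2/70 = 97.1% or 1 − 4/70 = 94.3%, with median half-widths of about 2.0 and 1.6 SD.

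The 4 v 4 size of 2.9% assumes common drift and equal spread of change. At SD ratios of 1.5, 2 and 3 it is 3.2%, 3.7% and 4.9%. If drift differs between groups by 0.25 or 0.5 SD, it is 3.5% or 5.5%.

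Over three unadjusted outcomes at 4 v 4, the chance of at least one false positive is 1 − (1 − 2/70)^3 = 8.3% if they are independent, 7.9% at correlation 0.5 and 6.6% at 0.8.

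**5. Controls alone.** A signed-rank test of treated against untreated change in four children has smallest p = 2/16 = 0.125. It can only be descriptive.

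**The case against.** **The practical gain is small.** Drift over 3 weeks may be slight, and at 0.1 to 0.25 SD the existing test rejects 4.5% to 7.5% of the time. The replacement has 14% power at 1 SD if 4 v 4. The authors may have meant the extra evaluation for description only. Much of this stands: the formal test adds little, and the estimate with its interval and the individual changes matter more. But a descriptive comparison is not stated either. Even with zero drift, the before-after test cannot show that drift was zero; an untreated interval can at least inform that.

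**It comes late.** Enrolment ended in October 2018, the document is dated September 2019, and the test is described in the past tense. An added comparison is probably post hoc and cannot restore pre-specification. This stands and must be labelled.

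**Stronger readings.** A reader might infer any of the following, and the documents support none of them.

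- *The error rate is badly inflated.* The 19% and 61% figures need drifts that nothing in the documents supports.
- *The trial lacks a controlled analysis.* The standardized assessments have a baseline-adjusted ANCOVA, and no section names the accelerometer outcomes as primary.
- *Bonferroni must be ruled out.* That is true at 4 v 4 and false at 8 v 4, and the group sizes are not given.
- *The accelerometer contrast is randomised.* How the children with accelerometers were chosen is not described.

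**Conclusion.** The omission is real, and I hold it with high confidence: the only stated accelerometer test has no untreated comparator, although an extra evaluation was made to provide for that comparison. This conclusion depends neither on who the eight are nor on any drift, because a before-after test of any eight children cannot attribute change to mCIMT.

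Its size is limited. It is a problem of attribution in the accelerometer subset, and the 16 v 16 ANCOVA is unaffected. The rejection rates rest on assumed drift and normal changes. The power, smallest p and interval figures depend on group sizes that the documents do not state, so confidence in the details of the remedy is lower. The plan should be corrected, with modest expectations of what the comparison can show.

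**What to change.** 1. **Define the data first.** State who the eight are, how many mCIMT children wore accelerometers, how they were selected, the order and length of the evaluation intervals, and which evaluation is pre-treatment for the controls. Call the contrast randomised only if selection did not depend on arm.
2. **Add the comparison.** For VMA, %MVPA and UR, compare change in the mCIMT accelerometer children with change over the controls' untreated interval. Lead with the Hodges-Lehmann estimate and its exact interval, stating the coverage, and give the exact rank-sum p beside it. Label it exploratory, and post hoc with a date if it was added after data were seen. Beside it, show each control's untreated and treated change without a test.
3. **Settle multiplicity by group size.** Either label the three outcomes unadjusted or use an adjustment that can work. At 8 v 4, Bonferroni can reject. At 4 v 4 it cannot; a joint permutation max-statistic is an option, with smallest p 2/70. It should use a continuous statistic such as a standardized mean difference. With rank sums, three outcomes can each be fully separated by a different split, and ties then raise the smallest p to 6/70 = 0.086.
4. **Keep the eight-child signed-rank result as descriptive**, and do not attribute it to mCIMT alone.

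The cost is SAP wording and a few lines of analysis, with no new data if the controls have an untreated interval as inferred. The downside is low power and wide intervals: a null result would say little, and the comparison cannot settle effectiveness alone.

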for this unexpected result was the age of participants (mean: 4.9 years). An animal study confirmed that early CIMT during the corticospinal tract (CST) refinement period is effective for motor performance, and no longer effective once the CST refinement period has passed.¹³ Considering that the myelination of the CST is complete by 3 years of age in humans,¹⁴ application of CIMT in infants and toddlers is expected to yield different results.

Study Objective

The main purpose of this study is to determine whether modified CIMT (mCIMT) with continuous restraint is feasible for infants and toddlers with unilateral CP and is effective in enhancing the amount of paretic arm use in the real world. The study is based on the hypothesis that mCIMT would be feasible and facilitate better use of the paretic hand in the real world.

Methods

Participants

Informed consent forms were obtained from the children's parents or legal guardians before enrollment. From November 2015 to October 2018, we prospectively enrolled consecutive children with unilateral CP who were admitted to a tertiary hospital in Seoul, Republic of Korea. The inclusion criteria were (1) age 7 to 36 months and (2) diagnosed with unilateral CP due to central nervous system lesions. The exclusion criteria were (1) severe cognitive dysfunction that rendered them unable to perform simple tasks (e.g., reaching, grasping), (2) untreated seizures, (3) visual or auditory problems interfering with treatment, and (4) prior history of musculoskeletal disorders. We asked parents to report if their child presented any adverse events such as sleep disorder or skin rashes. This study excluded

participants whose potential risks exceeded the efficacy, and those with absence rates >20% (>3/15 sessions).

Study design

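### The only effect measure planned for the between-group ANCOVA is partial eta-squared with band labels; no adjusted mean difference or confidence interval is planned

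*Combined protocol and SAP*

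**What the plan says.** All of the planned analysis is in one paragraph, headed Statistical analyses plan, in the combined protocol and SAP. The between-group comparison reads: "Differences between groups in standardized assessments at post-treatment will be compared with analysis of covariance using pre-treatment measures as covariates". Its stated purpose is to establish the treatment effect.

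The same paragraph adds a within-arm analysis: "pre- and post-treatment outcomes of standard assessments will be compared using paired t-test in each group". The accelerometer outcomes go to a Wilcoxon signed-rank test.

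On effect size it says: "Effect sizes will be expressed as partial eta-squared, which was calculated and reported as recommended by Cohen". The bands follow, in the sentence that opens "The ranges for effect sizes are small": .01 to .06 is small, .06 to .14 moderate, and above .14 large.

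Under Study design, the 32 children are "randomized into the mCIMT or control group by permuted block randomization with block length 4 (N=16 per group"). Under Participants, the study excludes "those with absence rates >20% (>3/15 sessions"), with no figure for how many children that removed. No alpha, sidedness, power, SD or minimal important difference is stated.

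**The concern.** The main product of a randomized comparison is an estimate of how far apart the arms are, in which direction, and how uncertain that is. Followed as written, this plan yields a p-value and a band label.

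- **Sign.** Partial eta-squared is the same whether mCIMT helps or harms, while the Study Objective states a directional hypothesis.
- **Scale.** The index is relative to residual variance, so one value can mean quite different gaps in scale points, depending on how strongly baseline predicts outcome.
- **Precision.** At this sample size the index varies widely from sample to sample, and no interval is planned to show it.

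The within-arm paired t-tests do not fill the gap. The children are 7 to 36 months old and both arms kept their existing therapy, so both arms may improve. The question is the difference between them.

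**Working it through.** The plan gives no power or effect-size figure to reproduce. The check is what an observed partial eta-squared would mean at this trial's size.

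**Inputs from the document:** 16 per group (Study design); band edges .01, .06 and .14; ANCOVA with the pre-treatment measure as covariate (Statistical analyses plan).

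**Assumptions:** one covariate per model, all 32 analysed, baseline balanced between arms, two-sided 5%. Error df = 32 - 3 = 29.

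**Formulas.** Let e be partial eta-squared.
- F = e × df / (1 - e)
- Adjusted difference in residual SD units: d = √(F × (1/n1 + 1/n2))
- 95% half-width = t(.975, df) × √(1/n1 + 1/n2)

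**Step 1: the band edges at 16 vs 16.** √(1/16 + 1/16) = 0.3536 and t(.975, 29) = 2.045, so the half-width is 0.723.

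| Observed e | F | p | d (residual SD) | 95% CI |
|---|---|---|---|---|
| .06 (moderate begins) | .06 × 29 / .94 = 1.851 | 0.184 | 0.481 | -0.242 to 1.204 |
| .14 (large begins) | .14 × 29 / .86 = 4.721 | 0.038 | 0.768 | 0.045 to 1.491 |

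At e = .06 the equal-tailed noncentral-F 95% interval for eta-squared, taking eta-squared as λ/(λ + 32), is 0 to 0.258. It runs from no effect well into the large band.

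**Step 2: where significance starts.** The critical F(1, 29) is 4.183, so the critical e is 4.183 / (4.183 + 29) = 0.126. The non-significant part of the moderate band is (0.126 - 0.06) / (0.14 - 0.06), about 83% of its width.

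**Step 3: labels when there is no effect.** Under the null, e follows Beta(1/2, 29/2). It exceeds .01 with probability 0.592, .06 with 0.184 and .14 with 0.038. Subtracting the 0.05 that are significant, 0.592 - 0.05 = 0.542 and 0.184 - 0.05 = 0.134 would carry a label with p ≥ .05. Any label above .14 would be significant.

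**Step 4: sign.** In one simulated 16 vs 16 data set the group effect and residuals were reversed. The adjusted difference went from +0.60 (0.18 to 1.02) to -0.60 (-1.02 to -0.18). Partial eta-squared was 0.226 both times.

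**Step 5: scale.** One residual SD equals √(1 - r²) raw SD, where r is the pre-post correlation, which the document does not give. For r = 0, .5, .7 and .9, e = .14 is 0.768, 0.665, 0.549 and 0.335 raw SD. The same label covers more than a twofold range (0.768 / 0.335 = 2.3).

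**Step 6: sensitivity.**
- *Two covariates (df 28):* e = .06 gives d = 0.473, CI -0.252 to 1.197, almost unchanged.
- *Absence rule removing mCIMT children only, 12 vs 16 (df 25):* half-width 0.786; e = .06 gives d = 0.482, CI -0.304 to 1.269, p = 0.218. The critical e becomes 0.145, so e = .14 has p = 0.055.
- *8 vs 16 (df 21):* half-width 0.900; e = .06 gives d = 0.501, CI -0.399 to 1.402, p = 0.260. The critical e becomes 0.171, so e = .14 has p = 0.079.

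The two attrition rows are illustrative, since the document gives no attrition figure.

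**The case against.** The strongest reply is that nothing in the plan is wrong. Baseline-adjusted ANCOVA is a sound analysis, and partial eta-squared is a legitimate companion to it. The p-value stands beside the label. At 16 vs 16 every large label would be significant, and most null results labelled small or moderate would be visibly non-significant. Nowhere does the plan say that the label replaces the test. The direction would hardly be unknown in practice either, because the ANCOVA coefficient has a sign and the paired t-tests show how each arm moved. The effect-size sentence also does not say which analysis it serves, and the document does not list the assessments that enter the ANCOVA.

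Much of this stands, and it limits the point to estimation and reporting. What is missing is a commitment to a signed, baseline-adjusted estimate with its uncertainty. A p-value does not supply that, and two within-arm changes are not a between-group estimate. The software can print adjusted means and intervals, but the plan does not say they will be reported. As for scope, ANCOVA is the only between-group outcome test, so attaching the effect-size sentence to it is the natural reading. On any other reading the ANCOVA would have no planned effect measure at all.

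**Conclusion.** The concern holds, as a low-priority improvement. For the between-group comparison of the standardized assessments, the plan commits to an unsigned, unitless index with band labels and to no estimate of precision. With 29 error df, a result at the start of the moderate band is compatible with anything from 0.24 residual SD in favour of control to 1.20 in favour of mCIMT, if the observed difference favours mCIMT. A result at the start of the large band is compatible with anything from 0.05 to 1.49.

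These figures rest on one covariate, all 32 children analysed, balanced baseline and a two-sided 5% level. Fewer children would widen the intervals; a second covariate changes little. The ANCOVA test and its type I error are unaffected. The point does not extend to the accelerometer outcomes, and it applies to whichever standardized assessments enter the ANCOVA.

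**What to change.** In the Statistical analyses plan, replace the effect-size sentence with one that makes the baseline-adjusted mean difference (mCIMT minus control), with its two-sided 95% CI in scale units, the effect measure for each standardized assessment analysed by ANCOVA. Partial eta-squared may stay as a supplement, optionally bias-corrected and with its own interval. The band label should not be the main interpretation.

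The cost is one sentence and one table column. Both quantities come from the ANCOVA already planned, and no new data are needed. There are two downsides. The wide intervals become visible, and scale-unit differences cannot be compared across assessments, which is the reason to keep eta-squared alongside.
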